### **Study configuration**

This study is designed as a single-arm study. All eligible candidates shall be enrolled to undergo treatment by the device according to the procedure and protocol that are discussed herein. This approach is consistent with other studies that have been done with similar devices where the primary objective of waist circumference reduction was also intended.

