**Efficacy of Low-Frequency, High-Intensity Ultrasound  
for Reduction in Subdermal Adipose Layers**

Device Investigated: Ultimate Contour Body Sculpting Device

Indication Studied: Application of ultrasound for non-invasive waist circumference reduction.

A randomized, blinded comparison of waist circumference reduction of an active test group vs. a placebo control in adults.

Sponsor: CAO Group, Inc.

Protocol ID: 005-00036-8

Development Phase: Performance Validation

NCT ID: Not Yet Assigned

Anticipated Initiation Date: 15 December 2019

Anticipated Completion Date: 1 May 2020

Document Date: 10 October 2019

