## **Statistical Methods**

Single factor ANOVA analysis will be used to determine if the extent of circumference reduction in the test group is statistically significant over changes in the control group. Additional correlation assessment will be performed to identify any potential relationships between patient data sets, and single-factor ANOVA assessment applied to those correlations as applicable. Missing or incomplete data shall be populated using least-favorable data from participants who did complete the study.

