## **STUDY OBJECTIVES**

**PRIMARY** - The primary objective of this study is to determine if the application of lower frequency (35kHz to 45kHz) ultrasound energy to the waist/abdominal region of the human body is capable of effecting a reduction in the amount of subcutaneous adipose cells and/or tissue to an amount of at least 1 inch and to a statistically significant level. Determination of the reduction in this adipose tissue is achieved via measurement of the body circumference that includes the abdominal area that was treated, and comparing measurements prior to the initial treatment with measurements after the entire treatment regime is concluded. Per the proposed clinical mechanism of action, the disrupted tissue is cleared by the lymphatic system which facilitates excretion or elimination of the disrupted tissue contents. Having been eliminated, the patient should exhibit a reduction in waist circumference. For this objective to be successfully achieved, a reduction in waist circumference of at least one inch must be demonstrated at a point of 12 weeks after the last of three treatment sessions has been applied.

**SECONDARY** - The secondary objective of this study is to assess the safety of this device. Assessment is made by having the patient rate the treatment experience and report any symptoms, side effects, or associated abnormal conditions. Additional assessment is made by the investigators to qualitatively confirm if visually detectable abnormal conditions (example: edema) are presented following the treatment. Success is determined by whether the patients indicate that any discomfort experienced during the treatment, and following the treatment that are directly attributable to the treatment, along with an absence of side-effects or abnormal conditions directly attributable to the treatment, create a risk/benefit condition where the benefit of treatment is regarded to outweigh the risks and temporary discomfort. Quantitatively, the benefit is regarded to outweigh the risk when: 1) No patients report a pain rating of 4 or higher on the Stanford Pain Scale, 2) No patients exhibit any side effects or abnormal conditions at the conclusion of the final treatment, and 3) No patient who was included in the Test group reports that the treatment regimen was unsuccessful.

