### **Statistical methods planned, including handling data exclusion, analysis of sub-groups if any**

Any patient that did not conclude all three treatments shall be excluded from the analysis. If there are fewer than 37 patients remaining after the study concludes and exclusions are applied, than no analysis shall take place and additional study subject enrolled until a minimum of 40 completed participants exist. In the event that a patient concludes at least one treatment session, but afterwards discontinues

participation in the study, the presence of the patient in the study shall be acknowledged for data analysis purposes. Missing data for such acknowledged participants shall be fulfilled by inserting the least favorable result obtained realized from among all test subjects who did complete the study. Statistical analysis shall then proceed on the fully populated study data.

Primary analysis shall consist of applying the Anova single-factor acceptance test evaluating the change in waist circumference based on the data collected by the tape measure. A confidence of  $P=0.05$  shall be applied. The results of this data shall be directly applied to determining if the primary objective of the study has been met.

A correlation analysis shall be applied to all variable data recorded, as well as key calculations from the data, to identify any potential two-way connections or relationships between sets of data. Any correlations scoring a magnitude of 0.85 or greater shall be discussed and if appropriate, Anova single-factor analysis applied to determine if there is statistical significance to the relationship and any statements that might be supported by the data. Of primary interest is any impact the starting BMI might have on the amount of change, and any impact that gender may impart to the outcome.

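### The plan describes both a randomized placebo comparison and a single-arm study, which leaves the primary test undefined and the stated 80% power fitting neither design

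*Combined protocol and SAP*

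**What the plan says.** All of the following is current text in the combined protocol and SAP.

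- **Title page:** "A randomized, blinded comparison of waist circumference reduction of an active test group vs. a placebo control in adults".
- **Synopsis, Statistical Methods:** a single-factor ANOVA is to "determine if the extent of circumference reduction in the test group is statistically significant over changes in the control group".
- **Study configuration:** "This study is designed as a single-arm study. All eligible candidates shall be enrolled to undergo treatment by the device".
- **Study Objectives, primary:** the effect is found by "comparing measurements prior to the initial treatment with measurements after the entire treatment regime is concluded", and must be shown "to an amount of at least 1 inch and to a statistically significant level" 12 weeks after the last session.
- **Statistical methods planned:** the primary analysis consists of "applying the Anova single-factor acceptance test evaluating the change in waist circumference based on the data collected by the tape measure", at P=0.05. No factor, level or comparator is named. Enrolment reopens, with a target of 40 completers, only "If there are fewer than 37 patients remaining after the study concludes and exclusions are applied". Analysis can therefore go ahead with 37.
- **Sample size:** a formula with a leading factor of 2 is said to give 37. That figure is treated as the whole study population, with a minimum total of 40 and 50 recruited.

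Group wording also survives elsewhere. The safety objective requires that "No patient who was included in the Test group reports that the treatment regimen was unsuccessful". The Sequence and duration section speaks of a patient's assigned study group, and the Monitoring section expects patients as well as staff to be blinded.

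**The concern.** A reader cannot tell from the plan whether there is a control group. The contradiction reaches the primary analysis and the sample-size basis, so it is more than a stale title. Three things are at stake.

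- **Choice of test.** If the study runs as a single arm, the comparison in the synopsis does not exist and the Data Analysis section does not supply a replacement. The analyst would have to choose the factor and the test with the data in hand.
- **Stated power.** The 80% describes neither of the two designs.
- **The conclusion.** The synopsis (Methodology) gives every patient diet and exercise advice after the last treatment. A single arm can therefore show only a before-after change with device plus advice. A report that carried over the title-page description would claim a control that the study lacks.

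**Working it through.** **1. Which design is described?** Study configuration says one arm. The Application of the Treatment section gives one set of active settings and no sham. No section gives a randomization method, an allocation ratio or a control procedure. The title page, the synopsis ANOVA, the safety objective, the Sequence and duration section and the Monitoring section all presuppose groups or patient blinding. The operational text supports one arm; the description, the synopsis analysis and the sample-size formula assume two.

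**2. Can the synopsis ANOVA be run?** With k groups, the between-group degrees of freedom are k - 1. For k = 1 this is 0, so there is no F statistic.

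**3. Reproducing the stated 37.** Inputs from Sample size: Z values 1.96 and 0.84, sigma = 1.50 inches, d = 1.0 inch.

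- Plan's formula: 2 × (1.96 + 0.84)² × 1.5² / 1.0² = 2 × 7.84 × 2.25 = 35.28, so 36.
- The t-based two-sample version gives 36.3, so 37.

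The stated figure reproduces, but as a number per arm: power by noncentral t is 79.7% at 36+36 and 80.8% at 37+37. The difference between 36 and 37 is not an error.

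**4. Power under each design.** Two-sided 0.05, true difference or change 1.0 inch, SD 1.5 inches, t-based:

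| Design | Completers | Power |
|---|---|---|
| Two arms, 1:1 | 37 (18+19) | 50.4% |
| Two arms, 1:1 | 40 (20+20) | 53.8% |
| Two arms, 1:1 | 50 (25+25) | 63.7% |
| One arm, change against zero | 37 | 97.6% |
| One arm, change against zero | 40 | 98.4% |

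For one arm against zero, 80% power needs (1.96 + 0.84)² × 1.5² / 1.0² = 17.64, so 18 by formula, or 20 by the exact t calculation (19.7 rounded up).

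**5. What could the ANOVA in the Data Analysis section mean?** Set beside the before-after definition in Study Objectives, two readings can be computed.

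- *Repeated measures, time as the factor.* With two time points F equals the square of the paired t, so power is that of the one-arm rows above.
- *Unpaired, pre values against post values.* This ignores pairing and puts the between-patient spread of waist size into the error term. With a between-patient SD of 3 inches and 40 patients, the standard error used is about √((9 + 9)/40) = 0.67 inch. Significance then needs an observed mean change of about 1.99 × 0.67 = 1.3 inches, although the true mean is 1.0. In simulation (40,000 trials per setting, n = 40, change with mean 1 and SD 1.5) this test was significant in 7-12% of trials at a between-patient SD of 3 inches, 0.4-0.5% at 4 inches, and 0.01% or fewer at 5-6 inches. The paired test on the same data was significant in 98%. The waist SDs are assumed, because the documents give none.

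**6. The 1-inch rule.** If the rule means an observed mean reduction of at least 1 inch, and the true mean is exactly 1 inch, the observed mean falls on either side of 1 about equally often. An observed mean of 1 inch with n = 40 and SD 1.5 gives t = 1 / (1.5/√40) = 4.2, so significance adds almost no further hurdle. Simulation of both conditions together gives 50.2% at n = 40 and 50.3% at n = 37. If the rule applies to each patient, about half of patients would meet it under the same assumptions.

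**The case against.** The strongest reply is that a single arm is a declared choice, which the plan calls consistent with earlier studies of similar devices, and that the rest is leftover wording. The first part stands: nothing here says that a control group must be added. The second does not, because the leftover wording includes the synopsis's primary comparison and the sample-size formula.

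Three stronger readings are tempting, and the documents do not support them.

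- **That the planned ANOVA must be the unpaired one and would almost certainly miss a 1-inch change.** The Data Analysis section never says unpaired, and change is a within-patient quantity. A repeated-measures ANOVA is also single-factor and loses nothing. What can be said is that the factor is unnamed and that power depends heavily on the choice. The very low figures hold for one reading only and rest on assumed waist SDs.
- **That 18-20 patients would do.** That number addresses significance against zero and leaves out the 1-inch requirement in Study Objectives. It does not justify a smaller study.
- **That 98% is the chance of meeting the primary objective.** It is the chance of significance against zero alone.

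A smaller point also stands. The synopsis statement that each patient is treated three times does not settle the design, since three sham sessions would fit it too. Study configuration and the Application of the Treatment section carry that argument.

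**Conclusion.** The concern holds and should be fixed before enrolment. The plan contradicts itself on whether there is a control group. The synopsis's primary comparison cannot be computed under the single-arm design, and the Data Analysis section does not define a substitute. A per-arm size of 36-37 is used as a study total, so 80% power is not what either design delivers: about 50-54% for two arms with 37-40 completers, and 97.6-98.4% for one arm against zero, with about a 50% chance of also meeting a mean-based 1-inch rule when the true mean change is 1 inch.

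These figures assume 1:1 allocation for two arms, that the 1.5 inches is the SD of the change, and a true effect of 1.0 inch. The documents state neither of the first two. The contradiction, the missing factor and the per-arm/total mismatch do not depend on any assumption about waist SDs. A reader might infer that the single-arm design is itself the error; it is a stated choice, and the fault is that the rest of the plan does not follow it.

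**What to change.** Reconcile the title page, synopsis Statistical Methods, Study Objectives, Study configuration, Sequence and duration, Monitoring, Statistical methods planned, and Sample size before enrolment.

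**If one arm is kept:**

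1. Remove the randomized, placebo, control-group, study-group and patient-blinding wording.
2. Replace the ANOVA in both statistical sections with a paired (one-sample) t-test and 95% CI on the change from baseline to 12 weeks.
3. State whether the 1-inch rule applies to the mean or to each patient.
4. Keep the planned 40 completers, but replace the two-group formula with a one-sample calculation. It should report power against zero (about 98%) and, separately, the chance of also meeting the 1-inch rule (about 50% if the true mean change is 1 inch and the rule is an observed mean of at least 1 inch).
5. Limit the conclusion to a before-after change with device plus lifestyle advice.

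This costs a text amendment and no extra patients. The price is the controlled claim on the title page.

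**If two arms are intended:** describe the randomization, the allocation ratio and the control procedure, and restate the power as about 50-54% at 37-40 completers. Reaching 80% would need 72-74 completers. At the synopsis ratio of 50 recruited to 40 completers that is 72 × 50/40 = 90 to 74 × 50/40 = 92.5 recruited. At the Sample size section's 50 to 37 it is 72 × 50/37 = 97.3 to 74 × 50/37 = 100. Recruitment would therefore rise from 50 to about 90-100.

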### **Sequence and duration of study period**

Patients will be scheduled according to each one's availability for the first of three treatment sessions. After each particular treatment, the patient will be scheduled for the next visit, with it being preferred that subsequent treatments occurring between 6-8 days into the future of the present treatment. Each patient is to receive 3 treatment sessions, with each session featuring the same device settings and conditions of application relative to which study group the patient is assigned to. Overall, the study treatments are anticipated to take about 6 weeks to accomplish. The patient is recalled 1 week, 4 weeks, and 12 weeks after the last treatment for follow-up evaluation.

### **Measurement tools and methods**

#### **CIRCUMFERENCE**

The patient's circumference will be measured via use of a Gulick II (Model: 67020) tape measure with constant-tension feature that is factory-calibrated by the manufacturer. The process of obtaining a measurement proceeds as follows:

1. The area of the body is exposed (in this case lifting up the shirt to expose the abdominal region).
2. The patient is informed to stand straight and to breathe normally, but to focus on steady shallow breaths.
3. The clinician applies the tape measure by locating the top of the hip bone (iliac crest) and positioning the tape just above this bony landmark, just where one finger can fit between the iliac crest and the lowest rib.
4. The clinician ensures that the tape measure is positioned horizontally, parallel to the floor.
5. Measurement is taken at the end of normal expiration.
6. At a signal from the clinician the patient is to pause at the conclusion of an exhale, at which point the clinician pulls the tape until the constant-tension feature is enabled. The clinician then observes the measurement value and documents this value in the treatment record.

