### **Methodology**

Samples of the test device (Ultimate Contour Mini by CAO Group, West Jordan, Utah, U.S.A.) will be provided for the test. The devices consist of a touch screen interface whereby the operator may select the intensity of the delivered energy and the duration of treatment. The device features a single output cable to which is attached the ultrasound handpiece assembly. For the purposes of this test, the duration of treatment will be set at 30 minutes, and the intensity set at Level 4 (the maximum the device is capable of).

Application of the ultrasound energy consists of applying a treatment gel or liquid to the patient's skin (to eliminate air gaps between the applicator and the skin) and gently kneading the skin in circular motions, slowly progressing across the surface of the treatment area, making methodical passes until the entire treatment area has been exposed, then returning to the origin point and repeating this application approach.

Following treatment, the patient will be asked regarding the extent of discomfort experienced during the ultrasound application, and assessment will be made by a blinded, independent evaluator whether a number of visible skin conditions are observed or experienced by the patient.

Prior to the first treatment, the patient's weight and height will be measured by the blinded, independent evaluator, and the patient's waist circumference measured using a constant-tension flexible tape measure. Each patient will be treated a total of three (3) times, with a gap of 6-8 days between each treatment. Prior to each treatment, the patient will be weighed. Following the final treatment, the patient will be advised of support mechanisms (healthy diet, exercise, and so forth) to support a successful outcome. At 1, 4, and 12 weeks after the last treatment, the patient will be recalled for a final measurement and review of any outstanding adverse events. Study success shall be determined by achieving at least 1 inch of waist reduction between the initial measurement and the 12-week follow-up.

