#### TREATMENT (total time of activity, 14-18 weeks - 4-6 weeks for the 1st, 2nd, and 3rd treatment applications, and 12-14 weeks following the 3rd treatment for follow-up visit):

##### Individual Treatment Session (approximately 70 minutes)

###### Prior to the Treatment (about 10 minutes):

- The patient is scheduled to arrive at the study site to undergo a treatment.
- The date of the treatment and the time of arrival will be documented in the treatment session record.
- During the first treatment only: The patient is given the Q-Pre Survey to fill out.
- The assigned pre-treatment investigator measures the waist circumference of the patient and documents this in the Pre-Treatment record, with these measurements being made by the blinded assessment clinician as described in the Measurement Tools and Methods section of this protocol.
- Prior to Treatments 2 and 3, the patient will be asked for the study diary, and the pre-treatment investigator shall review the diary and the patient's previous post-treatment Anticipated Effects and Adverse Event forms and discusses with the patient the items that are recorded about any abnormal body functions or observations that may be relevant to the treatment. If any are indicated, these will be documented in the patient record. Additional record shall be made by the investigator as to whether past events and observations have been resolved or are still unresolved.
- The patient is moved to the treatment area.

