**Post-Treatment Assessment (approximately 15 minutes):**

- The Post-Treatment assessing investigator observes the treated area for any redness, edema, swelling, or other indications specifically called for in the Anticipated Effects treatment record. The patient is asked for any unexpected sensations, for example sensations of high heat or of a "pins and needles" tingling effect in the tissue. These anticipated effects are documented in the treatment session record. Un-anticipated effects are recorded in the Adverse Event form.
- The patient is presented with the Stanford Pain Scale chart and asked to rate their overall pain and discomfort during the treatment. This is documented in the treatment session record.
- A waist circumference measurement of the abdominal region is made using the constant-tension tape measure. This measurement is recorded in the Post-Treatment Measurement record.
- The patient is provided with a study diary form, and instructed to document in the diary any unusual sensations, events, or bodily responses and to bring the form with them for the next visit.
- At the final treatment session only, the patient is provided with the Q-Post Survey to fill out.
- The patient is then scheduled for the next study session, and then excused.

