**FOLLOW-UP (approximately 15 minutes):**

- The patient is scheduled for and arrives at the study site at the appropriate time points 1, 4, or 12 weeks after the final treatment.
- The date of the visit and the time of arrival will be documented Post-Assessment Measurement and Anticipated Effects forms.
- For the 1-week and 4-week visits, the patient fills out the WaistQ-Post Survey. For the 12-week follow-up, the WaistQ-12 Survey is filled out.
- The patient will have their waist circumference measured and documented by an investigator assigned to the post-treatment measurement and assessment activity, as described in the Measurement Tools and Methods section of this protocol. The patient will be asked for the study diary, and the investigator shall review the diary and discuss with the patient the items that are recorded about any abnormal body functions or observations that may be relevant to the treatment. If any are indicated, these will be documented in the patient record. The

investigator will also review observations and adverse events documented in previous sessions and discuss these with the patient. Additional record shall be made by the investigator as to whether past events and observations have been resolved or are still unresolved.

- For the 4-week or 12-week follow-up visits, the patient is provided with a study diary form, and instructed to document in the diary any unusual sensations, events, or bodily responses and to bring the form with them for the next visit. The patient is then scheduled for the 4-week or 12-week follow-up visits as appropriate.
- At the 12-week follow-up, additional review is made of the patient's Medical History and Medication forms and any new content for these forms is noted therein and discussed with the patient. If the 12-week follow-up visit is concluded and Adverse Event forms indicate any unresolved adverse results for the patient, additional follow-up is scheduled as appropriate until all adverse results are concluded.

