### **Sample size**

A total sample size of a minimum of 40 patients was established for this study. This number is based on

$$n = \frac{2 \cdot (Z_\alpha + Z_\beta)^2 \cdot \sigma^2}{d^2}$$

where:

$Z_\alpha = 1.96$ , based on a confidence of  $P=0.05$  (false rejecting of a true null hypothesis),  
 $Z_\beta = 0.84$ , based on a power of 80% (failure to reject a false null hypothesis),  
 $d = 1.0$  inch reduction in waist circumference as a meaningful/successful change in measurement,  
 $\sigma = 1.50$  inches, based on the evidence presented by a published study under similar treatment parameters and conditions reporting a typical response of 0.75 inches through the umbilical region and assuming some of the population may not respond at all.

The resulting calculation gives a population size of 37. Accounting for possible attrition and adding a generous margin of safety, a recruitment size of 50 individuals is arrived at. Review of the data analysis shall be conducted by an independent entity to confirm the handling and calculation of data, and the conclusions drawn from the data regarding statistical significance.

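### Both waist measurements behind the primary endpoint are single tape readings; averaging three re-placed readings would be a cheap, minor gain in precision

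*Combined protocol and SAP*

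**What the plan says.** The measurement procedure (Measurement tools and methods, CIRCUMFERENCE) positions the tape by a bony landmark, levels it, waits for the end of a normal breath out and applies constant tension. It then closes: "The clinician then observes the measurement value and documents this value in the treatment record". It sets no number of repeats, no averaging and no tolerance for measuring again.

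The visit instructions add none:

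- Before each treatment: "The assigned pre-treatment investigator measures the waist circumference of the patient and documents this in the Pre-Treatment record".
- After each treatment: "A waist circumference measurement of the abdominal region is made using the constant-tension tape measure". This goes on a separate record.
- At weeks 1, 4 and 12: "The patient will have their waist circumference measured and documented by an investigator assigned to the post-treatment measurement and assessment activity".

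The endpoint uses two of these values: "Study success shall be determined by achieving at least 1 inch of waist reduction between the initial measurement and the 12-week follow-up" (Synopsis, Methodology). The primary objective likewise says that "a reduction in waist circumference of at least one inch must be demonstrated". The planned primary analysis is a single-factor ANOVA on the change in circumference.

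The Sample size section uses an SD of 1.50 inches and does not say whether this includes the error of reading the tape. Under Data quality assurance, the sponsor checks the tape's calibration certificate and its readings on rigid metal cylinders.

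**The concern.** A change score built from two single readings carries the error of both. Locating the iliac crest, judging a finger's width and catching the end of a breath will not come out the same each time, even with a trained clinician and a good tape. The cylinder check tests the instrument. It says nothing about how well a reading repeats on a person with a BMI of 25 or more.

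Two things are at stake. Some of the variance in the primary endpoint may be removable without recruiting anyone. And as written, the trial cannot estimate its own reading error, so the final report could not say how much of the spread in change is measurement. A missing baseline replicate cannot be recovered once treatment has started.

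**Working it through.** **Inputs from the Sample size section.** Z values 1.96 and 0.84; SD of change 1.50 inches; d = 1.0 "inch reduction in waist circumference as a meaningful/successful change in measurement".

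**Input not in the documents.** e, the SD of a single reading around the patient's true circumference on that occasion. I assume 0.25, 0.5 and 0.75 inch.

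**Step 1: the plan's own figure.** n = 2 × (1.96 + 0.84)² × 1.50² / 1.0² = 35.28, which rounds up to 36. The two-sample t-test version gives 36.3, which rounds up to the stated 37. The figure reproduces. The formula gives patients per arm of a two-arm comparison.

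**Step 2: variance of the change.** With m independent readings averaged on each occasion,

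Var(change) = true variance + 2e²/m.

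If 1.50 already contains single-reading error, going from m = 1 to m = 3 gives

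Var = 2.25 − 2e² × (1 − 1/3).

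- e = 0.25: 2.25 − 0.083 = 2.167, SD 1.47 (variance down 4%)
- e = 0.50: 2.25 − 0.333 = 1.917, SD 1.38 (down 15%)
- e = 0.75: 2.25 − 0.750 = 1.500, SD 1.22 (down 33%)

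The last case is extreme: 2 × 0.75² = 1.125, so reading error would be half of the planned variance of 2.25.

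**Step 3: power.** Two-sided 5% level, difference 1.0 inch, noncentral t. The documents give no allocation ratio. I show 20 v 20 (the 40 completers split equally, an assumption) and 36 v 36 (the formula result read as per arm).

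| | SD | 20 v 20 | 36 v 36 |
|---|---|---|---|
| As planned | 1.50 | 54% | 80% |
| Mean of three, e = 0.25 | 1.47 | 55% | 81% |
| Mean of three, e = 0.50 | 1.38 | 60% | 86% |
| Mean of three, e = 0.75 | 1.22 | 71% | 93% |

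**Step 4: the single-arm case.** The Study configuration section calls the trial single-arm, while the title page describes a randomised placebo comparison. With one arm of 40 completers tested against zero change, power at SD 1.50 is already about 98%, so averaging adds almost nothing.

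**Step 5: the other reading of 1.50.** If 1.50 excludes reading error, a single reading gives Var = 2.25 + 2e² and the mean of three gives 2.25 + 2e²/3. At 37 per arm (normal approximation), power for one reading against the mean of three is:

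- e = 0.25: 79.7% v 81.1%
- e = 0.50: 73.7% v 79.0%
- e = 0.75: 64.9% v 75.6%

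The documents do not say which reading of 1.50 applies.

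**The case against.** Averaging replicates could be recommended for almost any tape endpoint, and this plan already does much to limit error. It fixes posture, breathing, landmark, level and tension. It requires a licensed physician trained by the sponsor on the measurement tool, and it checks the tape. The size of any gain rests wholly on an assumed reading SD. At 0.25 inch it is about one percentage point. The large gains need 0.75 inch, which nothing in the documents supports. All of this stands, and it keeps the priority low. What remains is that standardising a procedure does not measure its repeatability, and no section does so.

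Three stronger readings are tempting, and the documents do not support them.

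- *Single readings cost the trial its planned power.* This is not shown. If 1.50 came from data with single readings, the stated 80% already allows for their error. The low 54% at 20 v 20 has a different cause: a per-arm formula result used as a total. Replicates do little to change that.
- *The tape is read only once per visit.* Treatment visits have a reading before and another after the application. These are not replicates: treatment comes between them, they go on different records and no rule combines them. The follow-up visits have one reading.
- *One misplaced tape can create or erase a success.* That assumes each patient is classified against the 1-inch mark. The objectives do not clearly define success patient by patient, and the primary analysis compares changes by ANOVA, where one misreading is diluted across the group.

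**Conclusion.** The point holds as a cheap improvement of minor priority. Each of the two endpoint values is one reading, and no rule calls for replicates. For any reading error above zero, averaging independent re-placed readings lowers the SD of change, so the direction is certain.

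The size is not. Over assumed reading SDs of 0.25 to 0.75 inch, and with reading error inside the 1.50, the gain is about 1 to 17 points of power at 20 v 20 and 1 to 13 points at 36 v 36. It is negligible if the trial is single-arm. These figures also assume independent errors between readings and a true difference of 1.0 inch. They describe precision above plan, not a deficit against it. No power figure is final until the single-arm and placebo-controlled descriptions are reconciled.

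**What to change.** In the CIRCUMFERENCE procedure, require three readings at least at baseline (before treatment 1) and at week 12, with the tape removed and re-placed between readings. Record all three, analyse their mean, and report the within-occasion SD. In the Sample size section, state whether 1.50 inches includes reading error.

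The cost is an estimated few minutes of the same assessor's time per measurement and two extra form fields; the documents give no timing for the measurement itself. The 10-minute slot before the first treatment also holds a survey, so visits may run slightly longer. No extra patients are needed and treatment is unchanged.

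One limit remains. The baseline and week-12 readings fall to different staff roles, and repeats by one assessor do not remove differences between assessors. Keeping the same assessor for a patient's two endpoint measurements, where the blinding arrangements allow, would address that part.
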